8.3 Safety reporting and medical management

8.3.1 Reporting of serious adverse events

All SAEs have to be reported, whether or not considered causally related to the investigational product, or to the study procedure(s). All SAEs will be recorded in the CRF.

If any SAE occurs in the course of the study, then Investigators or other site personnel inform the appropriate AstraZeneca representatives within one day i.e., immediately but **no later than 24 hours** of when he or she becomes aware of it.

The designated AstraZeneca representative works with the Investigator to ensure that all the necessary information is provided to the AstraZeneca Patient Safety data entry site within 1 calendar day of initial receipt for fatal and life threatening events and within 5 calendar days of initial receipt for all other SAEs.

For fatal or life-threatening adverse events where important or relevant information is missing, active follow-up is undertaken immediately. Investigators or other site personnel inform AstraZeneca representatives of any follow-up information on a previously reported SAE within one calendar day i.e., immediately but **no later than 24 hours** of when he or she becomes aware of it.

Once the Investigators or other site personnel indicate an AE is serious in the EDC system, an automated email alert is sent to the designated AstraZeneca representative.

If the EDC system is not available, then the Investigator or other study site staff reports a SAE to the appropriate AstraZeneca representative by telephone.

The AstraZeneca representative will advise the Investigator/study site staff how to proceed.

Investigators or other site personnel send relevant CRF modules by fax to the designated AstraZeneca representative.

For further guidance on the definition of a SAE, see Appendix B of the Clinical Study Protocol.

8.3.2 Pregnancy

All pregnancies and outcomes of pregnancy should be reported to AstraZeneca except for:

- If the pregnancy is discovered before the study patient has received any study drug
- Pregnancies in the partner of male patients.

If a pregnancy is reported, the investigator should inform the sponsor within 24 hours of learning of the pregnancy.

Abnormal pregnancy outcomes (eg, spontaneous abortion, foetal death, stillbirth, congenital anomalies, ectopic pregnancy) are considered SAEs.

8.3.2.1 Maternal exposure

If any pregnancy occurs in course of the study, then the Investigator or other site personnel informs the appropriate AstraZeneca representatives within 1day i.e., immediately but **no later than 24 hours** of when he or she becomes aware of it.

The designated AstraZeneca representative works with the Investigator to ensure that all relevant information is provided to the AstraZeneca Patient Safety data entry site within 1 or 5 calendar days for SAEs (see Section 9.2.5) and within 30 days for all other pregnancies. The same timelines apply when outcome information is available.

8.3.3 Overdose

Use of durvalumab in doses in excess of that specified in the protocol is considered to be an overdose. There is currently no specific treatment in the event of overdose of durvalumab and possible symptoms of overdose are not established.

- An overdose with associated AEs is recorded as the AE diagnosis/symptoms on the relevant AE modules in the eCRF and on the Overdose Case Report Form module.
- An overdose without associated symptoms is only reported on the Overdose CRF module

If an overdose on an AstraZeneca study drug occurs in the course of the study, then the Investigator or other site personnel inform appropriate AstraZeneca representatives immediately, or **no later than 24 hours** of when he or she becomes aware of it.

The designated AstraZeneca representative works with the Investigator to ensure that all relevant information is provided to the AstraZeneca Patient Safety data entry site.

For overdoses associated with a SAE, the standard reporting timelines apply, see Section 8.2.2. For other overdoses, reporting must occur within 30 days.

9. STATISTICAL CONSIDERATIONS

9.1 Statistical hypotheses

No formal hypothesis testing will be conducted.

9.2 Sample size determination

The primary endpoint of the trial is to demonstrate the safety profile of durvalumab in routine clinical practice as assessed by the incidence of adverse events (AEs) (Serious and Non-serious AEs) observed during trial.

The study is intended to provide information regarding the safety profile for patients in India, and will contribute additional information to the overall safety profile of durvalumab. Due to the small sample size, this study should not be directly compared to the data from any other country. In this study, we expect to recruit 100 patients from Stage III unresectable NSCLC patients as per the Indian HA approved indication to satisfy the Imfinzi MA conditional approval.

9.3 Populations for analyses

For purposes of analysis, the following populations are defined:

Population	Description
Enrolled	All patients who sign the ICF
Safety analysis set	All patients assigned to Study treatment and who take at least 1 dose of IMP.

9.4 Statistical analyses

Analyses will be performed by AstraZeneca or its representatives. A comprehensive statistical analysis plan will be developed and finalised before database lock and will describe the patient populations to be included in the analyses, and procedures for accounting for missing, unused, and spurious data. This section is a summary of the planned statistical analyses of the primary and secondary endpoints. Any deviations from this plan will be reported in the clinical study report.

11. SUPPORTING DOCUMENTATION AND OPERATIONAL CONSIDERATIONS

Appendix A Regulatory, ethical and study oversight considerations

A 1 Regulatory and ethical considerations

This study will be conducted in accordance with the protocol and with the following:

- Consensus ethical principles derived from international guidelines including the Declaration of Helsinki and Council for International Organizations of Medical Sciences (CIOMS) International Ethical Guidelines
- Applicable ICH Good Clinical Practice (GCP) Guidelines
- Applicable laws and regulations

The protocol, protocol amendments, ICF, Investigator Brochure, and other relevant documents (eg, advertisements) must be submitted to an IRB/IEC by the investigator and reviewed and approved by the IRB/IEC before the study is initiated.

Any amendments to the protocol will require IRB/IEC approval before implementation of changes made to the study design, except for changes necessary to eliminate an immediate hazard to study patients.

The investigator will be responsible for the following:

- Providing written summaries of the status of the study to the IRB/IEC annually or more frequently in accordance with the requirements, policies, and procedures established by the IRB/IEC
- Notifying the IRB/IEC of SAEs or other significant safety findings as required by IRB/IEC procedures
- Providing oversight of the conduct of the study at the site and adherence to requirements of 21 CFR, ICH guidelines, the IRB/IEC, European regulation 536/2014 for clinical studies (if applicable), and all other applicable local regulations

The study will be performed in accordance with the AstraZeneca policy on Bioethics and Human Biological Samples.

A 2 Financial disclosure

Investigators and sub-investigators will provide the sponsor with sufficient, accurate financial information as requested to allow the sponsor to submit complete and accurate financial certification or disclosure statements to the appropriate regulatory authorities. Investigators are responsible for providing information on financial interests during the course of the study and for 1 year after completion of the study.

A 3 Informed consent process

The investigator or his/her representative will explain the nature of the study to the patient or his/her legally authorised representative and answer all questions regarding the study.

Patients must be informed that their participation is voluntary. Patients or their legally authorised representative will be required to sign a statement of informed consent that meets the requirements of 21 CFR 50, local regulations, ICH-GCP guidelines and New Drug & Clinical Trial Rules, 2019where applicable, and the IRB/IEC or study centre.

The medical record must include a statement that written informed consent was obtained before the patient was enrolled in the study and the date and time the written consent was obtained. The authorised person obtaining the informed consent must also sign the ICF.

Patients must be re-consented to the most current version of the ICF(s) during their participation in the study.

A copy of the ICF(s) must be provided to the patient or the patient's legally authorised representative.

A 4 Data protection

Each patient will be assigned a unique identifier by the sponsor. Any patient records or data sets transferred to the sponsor will contain only the identifier; patient names or any information which would make the patient identifiable will not be transferred.

The patient must be informed that his/her personal study-related data will be used by the sponsor in accordance with local data protection law. The level of disclosure must also be explained to the patient.

The patient must be informed that his/her medical records may be examined by Clinical Quality Assurance auditors or other authorised personnel appointed by the sponsor, by appropriate IRB/IEC members, and by inspectors from regulatory authorities.

A 5 Committees structure

The safety of all AstraZeneca clinical studies is closely monitored on an on-going basis by AstraZeneca representatives in consultation with Patient Safety. Issues identified will be addressed; for instance this could involve amendments to the Clinical Study Protocol and letters to Investigators.

A 6 Dissemination of clinical study data

A description of this clinical trial will be available on http://astrazenecaclinicaltrials.com, http://www.clinicaltrials.gov and CTRI (http://ctri.nic.in/Clinicaltrials) as will the summary of the study results when they are available. The clinical trial summary of study results may also be available on other websites according to the regulations of India in which the study is conducted.

A 7 Data quality assurance

All patient data relating to the study will be recorded on electronic CRF unless transmitted to the sponsor or designee electronically (eg, laboratory data). The investigator is responsible for

verifying that data entries are accurate and correct by physically or electronically signing the CRF

The investigator must maintain accurate documentation (source data) that supports the information entered in the eCRF.

The investigator must permit study-related monitoring, audits, IRB/IEC review, and regulatory agency inspections and provide direct access to source data documents.

The sponsor or designee is responsible for the data management of this study including quality checking of the data.

Study monitors will perform ongoing source data verification to confirm that data entered into the CRF by authorised site personnel are accurate, complete, and verifiable from source documents; that the safety and rights of patients are being protected; and that the study is being conducted in accordance with the currently approved protocol and any other study agreements, ICH GCP, and all applicable regulatory requirements.

Records and documents, including signed ICFs, pertaining to the conduct of this study must be retained by the investigator for 15 years after study completion unless local regulations or institutional policies require a longer retention period. No records may be destroyed during the retention period without the written approval of the sponsor. No records may be transferred to another location or party without written notification to the sponsor.

A 8 Source documents

Source documents provide evidence for the existence of the patient and substantiate the integrity of the data collected. Source documents are filed at the investigator's site.

Data reported on the CRF that are transcribed from source documents must be consistent with the source documents or the discrepancies must be explained. The investigator may need to request previous medical records or transfer records, depending on the study. Also, current medical records must be available.

A 9 Publication policy

The results of this study may be published or presented at scientific meetings. If this is foreseen, the investigator agrees to submit all manuscripts or abstracts to the sponsor before submission. This allows the sponsor to protect proprietary information and to provide comments.

The sponsor will comply with the requirements for publication of study results. In accordance with standard editorial and ethical practice, the sponsor will generally support publication of multicentre studies only in their entirety and not as individual site data. In this case, a coordinating investigator will be designated by mutual agreement.

Authorship will be determined by mutual agreement and in line with International Committee of Medical Journal Editors authorship requirements.

Appendix B Adverse event definitions and additional safety information

B 1 **Definition of adverse events**

An adverse event is the development of any untoward medical occurrence in a patient or clinical study patient administered a medicinal product and which does not necessarily have a causal relationship with this treatment. An AE can therefore be any unfavourable and unintended sign (e.g. an abnormal laboratory finding), symptom (for example nausea, chest pain), or disease temporally associated with the use of a medicinal product, whether or not considered related to the medicinal product.

The term AE is used to include both serious and non-serious AEs and can include a deterioration of a pre-existing medical occurrence. An AE may occur at any time, including run-in or washout periods, even if no Study treatment has been administered.

B 2 Definitions of serious adverse event

A serious adverse event is an AE occurring during any study phase (i.e., run-in, treatment, washout, follow-up), that fulfils one or more of the following criteria:

- Results in death
- Is immediately life-threatening
- Requires in- patient hospitalisation or prolongation of existing hospitalisation
- Results in persistent or significant disability or incapacity.
- Is a congenital abnormality or birth defect
- Is an important medical event that may jeopardise the patient or may require medical treatment to prevent one of the outcomes listed above.

B3 Life threatening

'Life-threatening' means that the patient was at immediate risk of death from the AE as it occurred or it is suspected that use or continued use of the product would result in the patient's death. 'Life-threatening' does not mean that had an AE occurred in a more severe form it might have caused death (e.g., hepatitis that resolved without hepatic failure).

B4 Hospitalisation

Outpatient treatment in an emergency room is not in itself a serious AE, although the reasons for it may be (e.g., bronchospasm, laryngeal oedema). Hospital admissions and/or surgical operations planned before or during a study are not considered AEs if the illness or disease existed before the patient was enrolled in the study, provided that it did not deteriorate in an unexpected way during the study.

B 5 Important medical event or medical treatment

Medical and scientific judgement should be exercised in deciding whether a case is serious in situations where important medical events may not be immediately life threatening or result in death, hospitalisation, disability or incapacity but may jeopardize the patient or may require medical treatment to prevent one or more outcomes listed in the definition of serious. These should usually be considered as serious.

Simply stopping the suspect drug does not mean that it is an important medical event; medical judgement must be used.

- Angioedema not severe enough to require intubation but requiring iv hydrocortisone treatment
- Hepatotoxicity caused by paracetamol (acetaminophen) overdose requiring treatment with N-acetylcysteine
- Intensive treatment in an emergency room or at home for allergic bronchospasm
- Blood dyscrasias (e.g., neutropenia or anaemia requiring blood transfusion, etc.) or convulsions that do not result in hospitalisation
- Development of drug dependency or drug abuse

B 6 For oncology studies, the following may be used instead:

The grading scales found in the revised National Cancer Institute CTCAE latest version will be utilised for all events with an assigned CTCAE grading. For those events without assigned CTCAE grades, the recommendation in the CTCAE criteria that converts mild, moderate and severe events into CTCAE grades should be used. A copy of the CTCAE can be downloaded from the Cancer Therapy Evaluation Program website (http://ctep.cancer.gov). The applicable version of CTCAE should be described clearly.

It is important to distinguish between serious and severe AEs. Severity is a measure of intensity whereas seriousness is defined by the criteria in Appendix B 2. An AE of severe intensity need not necessarily be considered serious. For example, nausea that persists for several hours may be considered severe nausea, but not a SAE unless it meets the criteria shown in Appendix B 2. On the other hand, a stroke that results in only a limited degree of disability may be considered a mild stroke but would be a SAE when it satisfies the criteria shown in Appendix B 2.

B 7 A Guide to Interpreting the Causality Question

When making an assessment of causality consider the following factors when deciding if there is a 'reasonable possibility' that an AE may have been caused by the drug.

- Time Course. Exposure to suspect drug. Has the patient actually received the suspect drug? Did the AE occur in a reasonable temporal relationship to the administration of the suspect drug?
- Consistency with known drug profile. Was the AE consistent with the previous knowledge of the suspect drug (pharmacology and toxicology) or drugs of the same

Version 4.1, Date: 12 October 2022

pharmacological class? Or could the AE be anticipated from its pharmacological properties?

- De-challenge experience. Did the AE resolve or improve on stopping or reducing the dose of the suspect drug?
- No alternative cause. The AE cannot be reasonably explained by another aetiology such as the underlying disease, other drugs, other host or environmental factors.
- Re-challenge experience. Did the AE reoccur if the suspected drug was reintroduced after having been stopped? AstraZeneca would not normally recommend or support a re-challenge.
- Laboratory tests. A specific laboratory investigation (if performed) has confirmed the relationship.

In difficult cases, other factors could be considered such as:

- Is this a recognized feature of overdose of the drug?
- Is there a known mechanism?

Causality of 'related' is made if following a review of the relevant data, there is evidence for a 'reasonable possibility' of a causal relationship for the individual case. The expression 'reasonable possibility' of a causal relationship is meant to convey, in general, that there are facts (evidence) or arguments to suggest a causal relationship.

The causality assessment is performed based on the available data including enough information to make an informed judgment. With limited or insufficient information in the case, it is likely that the event(s) will be assessed as 'not related'.

Causal relationship in cases where the disease under study has deteriorated due to lack of effect should be classified as no reasonable possibility.

B8 Medication Error

For the purposes of this clinical study a medication error is an unintended failure or mistake in the treatment process for an AstraZeneca study drug that either causes harm to the participant or has the potential to cause harm to the participant.

A medication error is not lack of efficacy of the drug, but rather a human or process related failure while the drug is in control of the study site staff or participant.

Medication error includes situations where an error.

- occurred
- was identified and intercepted before the participant received the drug
- did not occur, but circumstances were recognize that could have led to an error

Version 4.1, Date: 12 October 2022

Examples of events to be reported in clinical studies as medication errors:

- Drug name confusion
- Dispensing error e.g. medication prepared incorrectly, even if it was not actually given to the participant
- Drug not administered as indicated, for example, wrong route or wrong site of administration
- Drug not stored as instructed
- Examples of events that **do not** require reporting as medication errors in clinical studies:
- Participant accidentally missed drug dose(s) e.g. forgot to take medication
- Accidental overdose (will be captured as an overdose)
- Participant failed to return unused medication or empty packaging
- Errors related to background and rescue medication, or standard of care medication in open label studies, even if an AZ product

Medication errors are not regarded as AEs but AEs may occur as a consequence of the medication error.

Appendix C Handling of Human Biological Samples

C 1 Chain of custody of biological samples

A full chain of custody is maintained for all samples throughout their lifecycle.

The Investigator keeps full traceability of collected biological samples from the patients while in storage at the centre until shipment or disposal (where appropriate).

The sample receiver keeps full traceability of the samples while in storage and during use until used or disposed of or until further shipment and keeps documentation of receipt of arrival.

C 2 Withdrawal of Informed Consent for donated biological samples

If a patient withdraws consent to the use of donated biological samples, the samples will be disposed of/destroyed, and the action documented. If samples are already analysed, AstraZeneca is not obliged to destroy the results of this research.

The Investigator:

- Ensures patients' withdrawal of informed consent to the use of donated samples is notified immediately to AstraZeneca
- Ensures that biological samples from that patient, if stored at the study site, are immediately identified, disposed of /destroyed, and the action documented
- Ensures the organization(s) holding the samples is/are informed about the withdrawn consent immediately and that samples are disposed of/destroyed, the action documented and the signed document returned to the study site
- Ensures that the patient and AstraZeneca are informed about the sample disposal.

AstraZeneca ensures the organizations holding the samples is/are informed about the withdrawn consent immediately and that samples are disposed of/destroyed and the action documented and returned to the study site.

C 3 International Airline Transportation Association (IATA) 6.2 Guidance Document

This section is not applicable as no biological samples shall be transported out of the study sites during the course of study.

Appendix D: Recommended Treatment Modifications for Durvalumab and Management Recommendations

Adverse Reactions	Severity ^a	DURVALUMAB Treatment Modification	Corticosteroid Treatment Unless Otherwise Specified
Immune-mediated pneumonitis	Grade 2	Withhold dose ^b	Initiate 1 to 2 mg/kg/day prednisone or equivalent followed by a taper
	Grade 3 or 4	Permanently discontinue	1 to 4 mg/kg/day prednisone or equivalent followed by a taper
Immune-mediated hepatitis	Grade 2 with ALT or AST >3- 5xULN and/or total bilirubin >1.5- 3xULN Grade 3 with AST or ALT ≤8xULN or total bilirubin ≤5xULN	Withhold dose ^b	Initiate 1 to 2 mg/kg/day prednisone or equivalent followed by a taper
	Grade 3 with AST or ALT >8xULN or total bilirubin >5xULN Concurrent ALT or AST >3xULN and total bilirubin >2xULN with no other cause	Permanently discontinue	
Immune-mediated colitis or diarrhea	Grade 2	Withhold dose ^b	Initiate 1 to 2 mg/kg/day prednisone or

Adverse Reactions	Severity ^a	DURVALUMAB Treatment Modification	Corticosteroid Treatment Unless Otherwise Specified
	Grade 3 or 4	Permanently discontinue	equivalent followed by a taper
Immune-mediated endocrinopathies: Hyperthyroidism	Grade 2-4	Withhold dose until clinically stable	Symptomatic management
Immune-mediated endocrinopathies: Hypothyroidism	Grade 2-4	No changes	Initiate thyroid hormone replacement as clinically indicated
Immune-mediated endocrinopathies: Adrenal insufficiency, Hypophysitis/hypopituitarism	Grade 2-4	Withhold dose until clinically stable	Initiate 1 to 2 mg/kg/day prednisone or equivalent followed by a taper and hormone replacement as clinically indicated
Immune-mediated endocrinopathies: Type 1 diabetes mellitus	Grade 2-4	Withhold dose until clinically stable	Initiate treatment with insulin as clinically indicated
Immune-mediated nephritis	Grade 2 with serum creatinine >1.5-3x (ULN or baseline)	Withhold dose ^b	Initiate 1 to 2 mg/kg/day prednisone or equivalent followed by a taper
	Grade 3 with serum creatinine >3x baseline or >3-6xULN; Grade 4 with serum creatinine >6xULN	Permanently discontinue	
Immune-mediated rash or dermatitis	Grade 2 for >1 week	Withhold dose ^b	Initiate 1 to 2 mg/kg/day prednisone or equivalent followed by a taper
	Grade 3 Grade 4	Permanently discontinue	
Immune-mediated myocarditis	Grade 2	Withold dose ^c	Initiate 2 to 4 mg/kg/day prednisone

Adverse Reactions	Severity ^a	DURVALUMAB Treatment Modification	Corticosteroid Treatment Unless Otherwise Specified
	Grade 3 or 4, or any Grade with positive biopsy	Permanently discontinue	or equivalent followed by a taper
Immune-mediated myositis/polymyositis	Grade 2 or 3 Grade 4	Withhold dose ^d Permanently discontinue	Initiate 2 to 4 mg/kg/day prednisone or equivalent followed by a taper
Infusion-related reactions	Grade 1 or 2	Interrupt or slow the rate of infusion	May consider pre- medications for prophylaxis of subsequent infusion reactions
	Grade 3 or 4	Permanently discontinue	

^aCommon Terminology Criteria for Adverse Events, version 4.03. ALT: alanine aminotransferase; AST: aspartate aminotransferase; ULN: upper limit of normal.

After withhold, Durvalumab can be resumed if the adverse reactions improved to \leq Grade 1 and the corticosteroid dose has been reduced to \leq 10 mg prednisone or equivalent per day.

^b Based on severity of the adverse reactions, Durvalumab should be withheld and corticosteroids administered. Consider increasing dose of corticosteroids and/or using other systemic immunosuppressants if there is worsening or no improvement. Upon improvement to ≤Grade 1, corticosteroid taper should be initiated and continued over at least 1 month.

^c If no improvement within 3 to 5 days despite corticosteroids, promptly start additional immunosuppressive therapy. Upon resolution (Grade 0), corticosteroid taper should be initiated and continued over at least 1 month, after which Durvalumab can be resumed based on clinical judgment.

^d Permanently discontinue Durvalumab if adverse reaction does not resolve to ≤Grade 1 within 30 days or if there are signs of respiratory insufficiency.

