6.6 Dose modification

All dose modifications should be documented with clear reasoning and documentation of the approach taken.

In addition, there are certain circumstances in which study drug should be permanently discontinued (Section 7).

Following the first infusion of study drug, subsequent administration of study drug can be modified based on toxicities observed. All toxicities will be graded according to CTCAE Version 4.03. Dose reductions are not permitted.

Dose modifications will not be required for AEs that are clearly not attributed to study drug (such as an accident) or for laboratory abnormalities that are not deemed to be clinically significant. Dosing may continue despite concurrent vitiligo of any AE grade. Based on the mechanism of action of Durvalumab leading to T-cell activation and proliferation, there is the possibility of observing irAEs (immune related Adverse Events) during the conduct of this study. Potential irAEs may be similar to those seen with the use of ipilimumab and nivolumab including immune-mediated enterocolitis, dermatitis, hepatitis, and endocrinopathies (Brahmer et al 2010, Hodi et al 2010). Patients should be monitored for signs and symptoms of irAEs. In the absence of an alternate aetiology (eg, infection or PD) signs or symptoms of enterocolitis, dermatitis, hepatitis, and endocrinopathy should be considered to be immune-related.

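### Appendix D's unlettered resumption sentence conflicts with note c for Grade 2 myocarditis, and its bearing on three endocrine rows is not stated

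*Protocol*

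**What the plan says.** Protocol Appendix D holds three kinds of text on when a withheld dose may be given again.

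- **Unlettered sentence under the table, between notes a and b:** "After withhold, Durvalumab can be resumed if the adverse reactions improved to" Grade 1 or lower, provided the corticosteroid has come down to no more than "10 mg prednisone or equivalent per day". It names no row.
- **Myocarditis, Grade 2:** the action cell reads "Withold dose ^c". Note c says: "Upon resolution (Grade 0), corticosteroid taper should be initiated and continued over at least 1 month, after which Durvalumab can be resumed", subject to clinical judgment. It sets no 10 mg/day threshold.
- **Hyperthyroidism; adrenal insufficiency with hypophysitis/hypopituitarism; type 1 diabetes, each at Grades 2 to 4:** "Withhold dose until clinically stable". These cells carry no footnote letter, no grade threshold and no steroid threshold.

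Two other rows help to bound the point. The row "Immune-mediated endocrinopathies: Hypothyroidism" calls for no change in dosing, so no resumption rule arises there. Note d, for myositis, begins "Permanently discontinue Durvalumab if adverse reaction does not resolve to" Grade 1 or lower within 30 days, which is the same grade threshold as the unlettered sentence.

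**The concern.** Whether to re-expose a patient after immune-mediated myocarditis is a safety decision, and here the answer depends on which line of one table the site reads. The trial has a single objective, safety, and runs at about 10 sites. Sites that read the table differently could handle like patients differently, and the number of doses each patient receives would then partly reflect that reading.

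The conflict is sharpest for myocarditis, because the grade threshold, the steroid condition and the timing all differ between the two texts. For the endocrine rows the difficulty is less a contradiction than an open question: does clinical stability end the hold by itself, or must the unlettered sentence be met as well?

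**Working it through.** The plan states no figure on this point, so there is none to reproduce. The check sets the rules side by side as yes/no conditions.

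**Rules, all from Appendix D**
- General (unlettered sentence): grade ≤ 1 and steroid ≤ 10 mg/day.
- Note c: grade 0 and a taper of at least 1 month done, assuming that clinical judgment then favours resuming.
- Endocrine row: clinically stable.

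**Myocarditis.** Current grade (0, 1, 2) × steroid ≤ 10 mg/day (yes/no) × taper of at least 1 month done (yes/no) gives 3 × 2 × 2 = 12 states. The rules disagree in 4:

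| Grade | Steroid ≤ 10 mg/day | Taper ≥ 1 month | General | Note c |
|---|---|---|---|---|
| 1 | yes | no | permits | does not |
| 1 | yes | yes | permits | does not |
| 0 | yes | no | permits | not yet |
| 0 | no | yes | does not | permits |

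The disagreement runs both ways, so neither text simply contains the other.

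**Endocrine rows.** Current grade (1, 2, 3) × steroid ≤ 10 mg/day × clinically stable gives 12 states, with disagreement in 6. In 5 the row permits and the general sentence does not: Grade 1, stable, above 10 mg/day (1 state), and Grade 2 or 3, stable, at either steroid level (4 states). In 1 the reverse holds: Grade 1, at or below 10 mg/day, not stable. Only the adrenal/pituitary row starts corticosteroids. If the other two rows are restricted to states at or below 10 mg/day, 3 × 2 = 6 states remain and 3 disagree: Grade 2 stable, Grade 3 stable, and Grade 1 not stable. If the conditions are read as cumulative, the contradiction goes, but the hold can then outlast what the row alone would give.

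All of these are counts of logical combinations, not probabilities or expected numbers of patients.

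**Is there a tie-breaker?** Section 4.2 only points to Appendix D. Section 6.6 says that "subsequent administration of study drug can be modified based on toxicities observed" but gives neither a resumption rule nor an order of precedence. Section 7.1 concerns discontinuation and ranks nothing in Appendix D. The SAP does not address resumption.

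**How far apart in time are the two myocarditis rules?** The documents do not settle this. As an illustration, assume body weight of 50 to 80 kg, a patient at Grade 0, and a linear taper to zero over 30 days from the row's starting range of 2 to 4 mg/kg/day. With starting dose S mg/day, the dose reaches 10 mg/day on day t = 30 × (1 − 10/S).
- 50 kg × 2 mg/kg: S = 100, t = 30 × 0.900 = 27.0 days, gap to day 30 = 3.0 days.
- 80 kg × 4 mg/kg: S = 320, t = 30 × 0.969 = 29.1 days, gap = 0.9 days.

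Under these assumptions the taper accounts for about 1 to 3 days of difference, no more than the ±3-day visit window. A taper that falls faster early on would widen the gap. The wait from Grade 1 to Grade 0 is a separate difference, and nothing in the documents allows it to be quantified.

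**The case against.** The strongest reply is that the sentence may not be general at all. The text was read from PDF, and the sentence stands directly before note b. Its content fits that note, which uses the same Grade 1 threshold and concerns corticosteroids but has no resumption clause of its own. If the printed sentence belongs to note b, it governs pneumonitis, hepatitis, colitis, nephritis and rash, and the conflict disappears. This is plausible, and it is why the printed layout must be checked. As the text stands, no letter or wording makes the link.

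A second reply is that a reader at the myocarditis row is sent by its letter to a complete rule, that the specific normally overrides the general, and that both texts only permit resumption. A site following note c breaches nothing. Indeed, under note c the taper starts only at Grade 0, so a patient still at Grade 1 would normally not yet be down to 10 mg/day. This stands in part: the conflict bites mainly where a site has not worked from note c. But no text says that note c overrides the sentence, and whether a site should work from note c alone is the very matter left open.

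Third, Section 2.3 mentions separate management algorithms supplied to sites, and Section 8 asks that immediate safety concerns be discussed with the sponsor. Either might resolve a given case. The algorithms are not in these documents, and Appendix D should be consistent on its own terms.

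Two stronger readings are tempting and not supported:
- A reader might infer that following note c costs at least 2 of the 10 planned doses (20%), since a month spans two fortnightly visits. That counts the whole taper as a difference, although the unlettered sentence also requires steroids to be brought down to 10 mg/day or less. Much of the taper is common to both rules.
- A reader might infer that the action-taken categories in SAP Table 14.2.1.2 need rewording. They record what was done with the drug and need no resumption criterion.

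**Conclusion.** The point holds for Grade 2 myocarditis. As the text reads, Appendix D gives two resumption rules that differ in grade, steroid condition and timing, with no order of precedence. The clearest case is a patient at Grade 1 on 10 mg/day or less, who meets the unlettered sentence and fails note c.

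For the three endocrine rows the point is secondary. Clinical stability is undefined and could be read as an addition to the unlettered sentence, so these rows should not be given equal weight with myocarditis.

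The size is qualitative: 4 of 12 logical states for myocarditis and 6 of 12 for the endocrine rows. The number of patients and the net effect on doses cannot be derived from the documents, and no sample-size or precision figure changes. The conclusion rests on two assumptions: that the printed sentence is as unrestricted as it reads here, and that no separate site document already settles the matter. It takes no view on which clinical rule is right.

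**What to change.** 1. Check the printed position of the unlettered sentence in Appendix D: part of note a, part of note b, or free-standing.
2. The clinical team must reconcile it with note c and with the three endocrine rows that withhold dosing, including what clinical stability means there and whether the sentence applies as well.
3. Attach the sentence by letter to the rows it governs, or add one line saying which text prevails.
4. Confirm that the separate management algorithms given to sites say the same.

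The cost is a wording change in one appendix table, with whatever amendment and site notification that entails. It needs no new data and no change to the SAP.
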